During the third week of the evaluation period, subjects will attempt to abstain from smoking for a five day period and will be seen daily to determine smoking status. These visits will occur on five consecutive days with the visits in most instances occurring Monday through Friday. Subjects will be told to smoke normally until the evening prior to the first of the abstinence assessment days and then to attempt to not smoke at all during the subsequent five days. At each visit, smoking status will be evaluated by measuring exhaled carbon monoxide (CO) concentrations with a value of < 5 ppm confirming abstinence. Each visit during this week will be scheduled in the afternoon in order to assess mid-day CO rather than CO after just waking up. Subject will stop taking medication after they complete their five consecutive days of study visits.

The same procedures will then be repeated except that subjects will receive the alternate treatment. Since continued participation in the study will require subjects to resume smoking, subjects will be told that it is not necessary for them to resume smoking if they wish to remain abstinent; however they would not be able to continue participation in the study if this were the case. At the conclusion of the study, subjects will be given information about resources in the community that could assist them with the smoking cessation attempt. They will additionally be called by telephone approximately 1 week after completing the study in order to ensure that there are no adverse events and to ascertain if they have attempted to quit smoking. Those that have not made a cessation attempt will be encouraged to do so and will again be provided with information regarding community resources to assist them.

Subjects will therefore be seen at a screening visit and at 9 visits per study period for a total of 19 visits.

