d) Justification for Drug Dosing: Subject will initiate levomilnacipran at 20 mg daily for 2 days and will then increase the dose to 40 mg once daily for the next 10 days. The recommended dose when used for the treatment of depression is 40 mg to 120 mg. A review of the clinical studies with levomilnacipran however demonstrates that there is little difference in antidepressant efficacy across the dosage range.¹⁴ Furthermore, smoking cessation studies assessing the efficacy of nortriptyline have used doses at the lower end of the recommended dosage range (smoking cessation studies have evaluated daily doses of 75 to 100 mg with the dosage range for depression being 75 mg to 150 mg per day). In order to minimize the risk of adverse events and in order to simplify the titration period (40 mg requires one dosage increase whereas 80 mg per day would require two dosage increases and 120 mg per day would require three dosage increases) we have decided to select a dose at the lower end of the therapeutic range but one that has clearly demonstrated efficacy when used in the treatment of depression. The duration of treatment is based on data demonstrating that bupropion and nortriptyline are successful at increasing smoking cessation rates after one week of treatment. Active medication and placebo will be prepared by the University of Minnesota Investigational Drug Services by over-encapsulating active drug and preparing matching placebo.

d) Subject recruitment and payment: Subjects will be recruited via the use of flyers and advertisements in local newspapers or on internet resources such as Craigslist. Additional recruitment avenues such as radio advertising will be used if necessary. Our research team has considerable experience recruiting subjects into smoking studies and has determined which advertisement strategies are most effective.

Subjects will receive \$20 for each visit that they complete with an additional \$15 bonus for each day of confirmed abstinence during the abstinence assessment visits occurring at week 3 of each medication period. Subjects who attend all study visits and comply with all study related procedures will receive a \$60 bonus (regardless of how successful they are at cessation). Subjects can therefore receive up to \$590 for completing the entire study.

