in the literature by others using these methods.⁵ With a total of 52 subjects completing the study (26 menthol smokers and 26 non-menthol smokers), we are able to detect an effect size of 0.57 standard deviations for the comparisons between levomilnacipran and placebo which is considerably smaller than the effect size of approximately 1.65 reported by Perkins et al for bupropion.⁵ Since we anticipate a 20% attrition rate, we are planning on enrolling 64 smokers in total (32 smokers of menthol cigarettes and 32 smokers of non-menthol cigarettes).

7 Data and Safety Monitoring Plan (DSMP)

The principal investigator in conjunction with the study physician will be responsible for monitoring adverse effects. At the conclusion of each visit subjects will be asked whether they have had any side effects. Any positive response will be followed up with questions regarding details of what the adverse effect was and the severity. To the extent possible, each adverse event will be evaluated to determine 1) its severity (mild, moderate, severe), 2) its relationship to the study medication; 3) its duration and 4) whether it constitutes a serious adverse event.

The participation of any subject will be discontinues if they develop a side effects of greater than moderate severity (as determined by the investigators) or develops any symptoms that in the opinion of the investigators would warrant discontinuation from the study. Participation in the study would also be discontinued if during the course of the study the subject develops a significant medical condition (regardless of whether it can be attributed to the study drug) or is initiated on medication that can be expected to interact with the measures being assessed or increase the risk of being on the study medication. The subject has the option of discontinuing their participation at any time for any reason. Adverse events will be reported to the IRB as required per IRB guidelines.

8 References

1. Fiore MC, et al. *Treating tobacco use and dependence: 2008 Update. Clinical Practice Guidelines. U.S. Department of Health and Human Services. Public Health Service*. Rockville, MD2008.
2. Hughes JR, et al. Antidepressants for smoking cessation. *Cochrane Database Syst Rev*. 2014;1:CD000031.
3. Perkins KA, et al. An efficient early phase 2 procedure to screen medications for efficacy in smoking cessation. *Psychopharmacology (Berl)*. 2014;231:1.

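### A subject withdrawn by the investigators for safety forfeits the $60 completion bonus, a modest motive to understate side effects severe enough to end participation

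*Combined protocol and SAP*

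**What the plan says.** All references are to the combined protocol and SAP.

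- **Payment (section 4, d, Subject recruitment and payment).** Every completed visit earns $20. A further $15 is paid as a "bonus for each day of confirmed abstinence during the abstinence assessment visits occurring at week 3 of each medication period". The completion bonus is separate: "Subjects who attend all study visits and comply with all study related procedures will receive a" $60 bonus, and this holds "regardless of how successful they are at cessation". The stated maximum is $590.
- **Visits (section 4, c.2, Experimental Protocol).** "Subjects will therefore be seen at a screening visit and at 9 visits per study period for a total of 19 visits".
- **Withdrawal for safety (section 7, DSMP).** "The participation of any subject will be discontinues if they develop a side effects of greater than moderate severity". The investigators judge severity and may also withdraw a subject for other symptoms or for a significant new medical condition.
- **How side effects are found (section 7).** Staff ask the subject at the end of each visit and follow up any positive answer. The only physical examination described is at screening (section 4, c.1), and no on-treatment vital-sign measurement is described.

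The supplied text does not pro-rate the $60 and makes no exception for a subject whom the investigators withdraw.

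**The concern.** Read together, the attendance condition and the withdrawal rule attach a price to a candid answer. A subject who describes an effect that the investigators judge to be above moderate is withdrawn, cannot attend the remaining visits, and so cannot meet the bonus condition, even with perfect attendance up to that day.

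Two uses of the data depend on that answer. The first is subject protection, since the subject's report is the only on-treatment safety detection described. The second is the comparison of adverse event frequency between treatments (section 6, a.2 and a.4). If severe effects were understated, both would be weakened. The primary comparison of abstinent days is not directly affected.

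**Working it through.** **Inputs.** $20 per completed visit; $15 per confirmed abstinent day; $60 completion bonus (section 4 d). There is 1 screening visit and 9 visits per period, made up of 2 in the baseline week, 2 in the titration week and 5 in the quit week (section 4, c.2).

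**Reproducing the plan's figure.** Visits: 1 + 2 × (2 + 2 + 5) = 19. Maximum pay: 19 × $20 + 10 × $15 + $60 = $380 + $150 + $60 = $590, as stated.

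**Pay forgone on withdrawal after visit k.** Number the visits 1 to 19, so that the quit-week visits are 6–10 and 15–19. For k below 19:

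- Lower end (no abstinent day in the remaining quit visits): $20 × (19 − k) + $60.
- Upper end (abstinent at every remaining quit visit): the lower end + $15 × (quit visits remaining).

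| Withdrawn after | Visits left | Quit visits left | Pay forgone | $60 as share |
|---|---|---|---|---|
| Visit 5 (second week-2 visit, period 1) | 14 | 10 | $280 + $60 = $340, to $340 + $150 = $490 | 60/490 = 12% to 60/340 = 18% |
| Visit 10 (end of period 1) | 9 | 5 | $180 + $60 = $240, to $240 + $75 = $315 | 60/315 = 19% to 60/240 = 25% |
| Visit 18 | 1 | 1 | $20 + $60 = $80, to $80 + $15 = $95 | 60/95 = 63% to 60/80 = 75% |
| Visit 19 | 0 | 0 | $0 | none |

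Check at visit 5: pay already earned is 5 × $20 = $100, and $100 + $490 = $590.

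**Reading the table.** Everything except the $60 is pay for visits not made or abstinent days not recorded. The $60 is different: the subject has attended every visit open to them and loses it because the investigators ended their participation. It is a small part of the loss early in the study and most of the loss near the end.

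**Where the motive applies.** It needs an effect likely to lead to withdrawal, with at least one visit left. An effect reported as mild or moderate does not meet the severity trigger.

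**The case against.** The case on the other side is substantial.

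- **Not being paid for visits not made is ordinary.** This stands. The full $340–$490 should not be read as a penalty for reporting; only the $60 is at issue, about 10% of the maximum (60/590).
- **Under-reporting is an inference.** This stands. The documents give no rate of severe effects and no evidence that subjects conceal them. A reader might infer that harms will be under-reported mainly on levomilnacipran. The payment rule is the same in both double-blind periods, and that reading would need severe effects to be commoner on drug, for which the plan gives no figure.
- **There are safeguards.** The investigators judge severity and see subjects in person at 9 visits per period. A telephone call about one week after completion also asks about adverse events, when no visit pay is at stake. These reduce the motive's effect but do not remove it, and the call comes after treatment has ended.
- **The bonus supports retention.** This is legitimate where 52 completers are wanted. But a subject whom the investigators have withdrawn cannot be retained, so withholding the $60 from that subject buys no data.

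Two stronger readings are tempting. One is that the rule contradicts the assurance that the bonus is paid "regardless of how successful they are at cessation". It does not: the phrase concerns the number of abstinent days, and subjects with 0 or 10 such days both qualify if they attend. The other is that the plan misleadingly pays people to resume smoking. Section 4, c.2 says that "subjects will be told that it is not necessary for them to resume smoking if they wish to remain abstinent" and, in the same sentence, that they could not then continue. The consequence is disclosed, it follows from the cross-over design, and the $15 per day rewards abstinence within each quit week.

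**Conclusion.** The point holds in a limited form. As written, a subject withdrawn by the investigators for safety with visits remaining loses the $60 despite full attendance up to that point. This creates a modest, inferred motive to understate effects severe enough to cause withdrawal, in a trial whose described on-treatment safety detection is the subject's own report. The bonus is 12–18% of the pay forgone early in period 1 and 63–75% after visit 18.

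The conclusion assumes that the all-visits condition is applied literally and that no exception exists elsewhere. The consent form was not supplied and may contain one; if so, section 4 d) should match it. The documents do not support a claim that harms are in fact under-reported, or that the primary result is compromised.

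Whether to pay the bonus to subjects who leave after period 1 to remain abstinent is a separate matter. It would ease departure of those who succeeded in period 1, who would then have no period-2 value for the paired analysis in section 6, a.4, and it would rest on an intention that cannot be verified. That is a trade-off for the sponsor to weigh, not an error to correct.

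**What to change.** In section 4 d), after the bonus sentence, add that a subject discontinued by the investigators for a side effect or medical reason still receives the $60, provided every visit scheduled up to that point was attended. Tell subjects this at consent, after checking the consent form for any existing rule. Visits, eligibility and the withdrawal rule stay as they are.

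**Cost.** $60 per such withdrawal. The plan does not split its anticipated attrition by reason. As an illustration, if all 64 − 52 = 12 planned drop-outs were of this kind, the total would be 12 × $60 = $720; the actual number should be smaller.

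**Downside.** A subject who wants to leave gains a slight motive to overstate an effect. This is limited because the investigators, not the subject, determine severity. The change also leaves the ordinary loss of later visit pay in place, so it removes only the part of the motive that comes from the bonus.

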c.1) Screening visit: Initial eligibility will be assessed via a phone interview. Those likely to qualify will be scheduled for a screening visit at which written informed consent will be obtained and eligibility confirmed. Psychiatric exclusion will be based on the Primary Care Evaluation of Mental Disorders (PRIME-MD) instrument. The PRIME-MD, designed to be administered by non mental health professionals, has been found to have good agreement with assessments made independently by mental health professionals.¹³ Medical history will be obtained via subject report and a physical exam will be performed to ensure that subjects are in generally good health. A urine pregnancy test will be given to females to confirm that they are not pregnant. Following the screening visit, those subjects who qualify will be scheduled for the remainder of their visits.

c.2) Experimental Protocol: Subjects will participate in two evaluation periods each lasting three weeks. During one of the evaluation periods levomilnacipran will be evaluated whereas during the other evaluation period, placebo will be evaluated. Procedures for the two evaluation periods will be identical, with the order of which period occurs first (i.e. medication or placebo) assigned randomly. The procedures at each study visit are based on published methods. The first week of each period will consist of baseline smoking assessment. This week will also serve as a medication washout period when occurring as the first week of the second three week assessment period (with a terminal half-life of approximately 12 hours,¹¹ this should be a sufficiently long washout period). During this week subjects will be seen at the research clinic twice. At the second baseline week visit subjects will receive their initial supply of medication. Levomilnacipran will be dosed at 20 mg once daily for two days followed by 40 mg once daily for 10 days. This is consistent with the recommended dose for the treatment of depression.

During the second week of the evaluation period, subjects will begin to take their assigned medication (i.e. levomilnacipran or placebo) and will be seen at two visits. At the first of these visits, subjects will receive a supply of the 40 mg dose of medication (or placebo). Adverse events and subjective measures such as craving and withdrawal symptom severity will be assessed at each visit.

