a.4) Data analysis: A paired t-test will be used to test treatment effect based on days of abstinence per quit assessment week (range 0-5, not necessarily consecutive) between levomilnacipran and placebo. Additional separate analyses for menthol and non-menthol cigarette smokers will be conducted. A two-sample t-test will be used to compare the difference in days of abstinence per quit assessment week for menthol cigarette smokers compared to non-menthol cigarette smokers.

Repeated measures Analysis of Variance (ANOVA) will be used for days of abstinence per quit assessment week, assuming mixed effects three-factor ANOVA model (“Order of phases” with two levels, “Treatment” with two levels, “Menthol cigarettes smoker” with two levels, subject effects are random); then use contrasts to compare treatment with placebo for all participants and for menthol cigarette smokers and non-menthol cigarette smokers separately. This approach allows us to investigate primary and secondary aims simultaneously, therefore, to potentially achieve higher statistical power. The use of paired t-tests, on the other hand, provides a proper tool for sample size determination as seen in the following section.

Generalized estimating equation (GEE) model will be used to analyze the longitudinal data, with the number of subjects able to maintain continuous abstinence on all 5 days throughout the quit week as the secondary outcome. Treatment effect (levomilnacipran vs. placebo) and cigarette type effect (menthol vs. non-menthol) will be estimated.

Secondary variables such as scores on the MNWS, SSS and QSU-Brief will be summarized by the mean, standard deviation, median and range. The change in these measures occurring between baseline (i.e. the first week of treatment) and the last day of the third week will be compared between drug and placebo. Similar two-factor ANOVAs will be used to analyze each of the calculated differences as the primary endpoint. Additionally, frequency of subject reported adverse events will be compared between treatments via the use of paired t-tests.

a.5) Power Consideration: The adequacy of planned sample sizes are assessed using two-sided paired t-test. We tested the “minimum detectable difference”, expressed as the number of standard deviations (i.e. “effect size”) for several sample sizes where the two-sided paired t-test is pre-set at a 5% significance level and 80% power. The variability is based on estimates found

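### The paired t-test on days abstinent ignores period and needs both quit weeks; the mixed ANOVA might repair this, but it is neither designated primary nor fully specified.

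*Combined protocol and SAP*

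**What the plan says.** Section 6 a.4 (Data analysis) gives more than one analysis of the primary outcome.

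- **Paired test.** "A paired t-test will be used to test treatment effect based on days of abstinence per quit assessment week". Separate analyses by cigarette type follow.
- **Menthol comparison.** "A two-sample t-test will be used to compare the difference in days of abstinence per quit assessment week" between menthol and non-menthol smokers.
- **Mixed ANOVA.** A repeated measures analysis "assuming mixed effects three-factor ANOVA model", with factors *Order of phases*, *Treatment* and *Menthol cigarettes smoker* and random subject effects; "then use contrasts to compare treatment with placebo for all participants and for menthol cigarette smokers and non-menthol cigarette smokers separately". The reason given is "This approach allows us to investigate primary and secondary aims simultaneously", with possibly higher power. The paired t-test is then described as suitable for sample size determination.
- **GEE** for five-day continuous abstinence: "Treatment effect (levomilnacipran vs. placebo) and cigarette type effect (menthol vs. non-menthol) will be estimated". Neither order nor period is mentioned.

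Two parts of Section 4 c.2 (Experimental Protocol) bear on this. Randomisation is described as "with the order of which period occurs first (i.e. medication or placebo) assigned randomly", so order there means sequence. Subjects are told after period 1 that they need not resume smoking, "however they would not be able to continue participation in the study if this were the case".

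No analysis set or missing-data rule is given.

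**The concern.** A two-period crossover can have a period effect. Here period 2 is a second quit attempt within weeks of the first. A paired t-test on drug-minus-placebo differences leaves any such effect in the error term, as does the two-sample test of those differences.

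Whether the ANOVA removes it depends on points left open. If *Order of phases* means sequence, as order does in Section 4 c.2, its main effect varies only between subjects and does not adjust the within-subject treatment contrast. Period is adjusted for only if the factor means first or second phase, or if order x treatment is also fitted. The by-menthol contrasts need a treatment x menthol term that is not listed, so the factor list is not the full model and cannot settle the matter.

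The second issue is who is analysed. Every subject is motivated to quit (Section 4 c, Subjects), and those who wish to stay abstinent leave. The subjects most likely to be lost may therefore be those with the best period-1 result. A paired test has no place for them, and nothing says whether the ANOVA keeps them.

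What is at stake is mainly power in the by-cigarette-type comparisons, which Section 6 a.1 makes part of the primary aim. Section 1 would read a negative result as evidence against the mechanism, so a false negative matters.

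**Working it through.** **1. The plan's own figure.** Inputs from Section 6 a.5: two-sided 5%, 80% power, 52 completers (26 per cigarette type), detectable effect 0.57 SD. Noncentral-t power for a paired t-test gives 0.572 SD at n=26 and 0.396 SD at n=52. The stated 0.57 is thus the figure for one cigarette type, and the by-type tests have no spare power at that effect.

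**2. Cost of omitting period, balanced orders.** Let the within-subject difference have SD 1 and the period effect (period 2 minus period 1) be p in those units. Drug-first differences centre on d - p and placebo-first on d + p. The mean is still d, so there is no bias. The sample variance, however, estimates about 1 + p², so the standard error is overstated by √(1 + p²). Hence

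power ≈ Φ(d√n − t·√(1 + p²)), with t = 2.008 (n=52) or 2.060 (n=26).

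For n=52, d=0.396, p=0.5: Φ(2.856 − 2.008 × 1.118) = Φ(0.611) ≈ 73%.

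Simulation, 100,000 trials per cell (paired / period-adjusted power):

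| p (assumed) | n=52, d=0.396 | n=26, d=0.572 |
|---|---|---|
| 0 | 80.2 / 80.2% | 80.2 / 80.0% |
| 0.25 | 78.3 / 80.0% | 78.1 / 79.7% |
| 0.5 | 72.7 / 80.0% | 72.4 / 79.8% |
| 0.75 | 63.4 / 80.1% | 62.9 / 80.0% |

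With no drug effect, p=0.5 and n=52, the paired test rejects 2.9% of the time against 5.0% with adjustment: conservative, not inflated. The two-sample menthol test (26 v 26, d=0.792) behaves the same way: 79.9, 78.2, 72.6 and 63.1%, against about 80% with adjustment.

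**3. Does the ANOVA as listed help?** With treatment x menthol but without order x treatment, the overall contrast at n=52 has power 79.8, 78.1, 72.5 and 63.2% across the same four period effects. Adding order x treatment gives 79.7, 79.9, 79.8 and 80.2%. In one simulated balanced data set, the model with treatment, order and menthol gave the paired t-test's standard error (0.149). Adding treatment x menthol left it at 0.148. Adding period, or order x treatment instead, reduced it to 0.140 in both cases, because the two terms are aliased.

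**4. Whole trials of 64 enrolled.** With 20% random loss and a 1.0-day drug effect, power is 95.6% (paired) v 96.1% (mixed, all data) with no period effect. With a 1.0-day period effect (about 0.5 SD) it is 88.6% v 94.3%.

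**5. Selective exit.** Assumptions: placebo mean 1.85 days; all-five-day abstinence 14% on placebo and 23–30% on drug; 8% random loss; a stated share of period-1 five-day abstainers leaving. The ranges cover three true drug effects: 1.0 day uniform, 0.6 day uniform, and 0.6 in 30% of subjects.

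| Exit among five-day abstainers | Completer bias | Mixed model, all data |
|---|---|---|
| 25–40%, both orders | 0% to -6% | -1.3% to +1.9% |
| 40% drug-first, 20% placebo-first | -4% to -10% | -1.0% to +0.7% |
| 20% drug-first, 40% placebo-first | +1% to +3% | -0.9% to +0.7% |
| 40%, drug-first only | -7% to -14% | -0.8% to +0.7% |
| 40%, placebo-first only | +5% to +8% | -0.6% to +0.5% |
| Equal by order, also rising with an unobserved tendency to abstain | 0% to +4% | +2% to +5% |

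For scale, a 6% attenuation of 0.57 SD gives 0.57 × 0.94 = 0.536. Power then goes from 80% to 75% at n=26 and from 98% to 97% at n=52.

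Selective exit also unbalances the orders, and the unadjusted paired mean then picks up p × (placebo-first − drug-first)/N. With 40% exit in both orders, 81% of drug-first and 87% of placebo-first subjects complete. The fraction is (0.87 − 0.81)/(0.87 + 0.81) ≈ 4% of any period effect.

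**6. What restrains exit.** From Section 4 d (Subject recruitment and payment), leaving after period 1 forfeits up to 9 × 20 + 5 × 15 + 60 = 315 dollars of 19 × 20 + 10 × 15 + 60 = 590.

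**The case against.** The strongest reply is that the ANOVA already deals with this. It is a random-subject model, it is said to serve both aims, and the paired t-test is justified as a sample-size tool. Under two ordinary readings (order means first or second phase, or a three-factor ANOVA includes its interactions) period is adjusted for. This shows the defect is not certain. It does not remove it: Section 6 a.4 still says the paired test will be used for the treatment effect, Section 4 c.2 uses order for sequence, and no interaction is listed.

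The objection on size largely stands. The n=52 losses in the table are set at 0.396 SD, which the plan does not state. At its 0.57 SD with all 52 completers, power is 98.1% with no period effect and 97.7, 96.6 and 94.0% at 0.25, 0.5 and 0.75 SD. At n=26 and 1.0 SD it stays above 99%, and at the 1.65 SD benchmark the loss is negligible. The paired, ANOVA and two-sample losses are one mechanism, not three harms.

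On exit, the larger biases need exit to differ by order, which double-blinding makes less likely. If exit follows an unobserved tendency equally in both orders, the mixed model brings no gain. That the paired test drops one-period subjects is inferred from the method and the completer-based sample size, not stated.

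The GEE sentence lists effects to be estimated and need not list every covariate. It is a gap in specification, with no consequence calculated here.

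**Conclusion.** The concern holds, as a cheap improvement rather than a flaw that threatens validity. With balanced orders the type I error is not inflated and the estimate is not biased by period. The material loss is in the by-cigarette-type tests near 0.57 SD: about 2, 8 and 17 percentage points of power at assumed period effects of 0.25, 0.5 and 0.75 SD. For all 52 at 0.57 SD the loss is at most about 4 points over that range. Selective exit adds little if equal in both orders; if it is heavier drug-first, the drug effect is attenuated by about 4% to 14% in the scenarios run.

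The documents give neither a period effect nor an exit rate by outcome, so confidence in the size is medium. That the text leaves primary status, period adjustment and the analysis set open does not depend on these assumptions.

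**What to change.** In Section 6 a.4:

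- Designate as primary one mixed model with fixed treatment, period (first/second), order, menthol and treatment x menthol, and a random subject effect. Do not add order x treatment, which is aliased with period.
- Fit it by REML to all randomised subjects with at least one quit week, including those with period 1 only.
- Take the overall, menthol, non-menthol and menthol-comparison contrasts from this model.
- Add period to the GEE.
- Report exits after period 1 by order, and how many of those subjects said they wished to remain abstinent.
- Keep the paired t-test as a completer sensitivity analysis.

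The cost is wording and one degree of freedom (80.2% v 80.2% power at n=52 with no period effect); no visits or measurements are added. The model assumes missing at random given the observed period-1 result. If that fails equally in both orders, it can lie 1 to 3 percentage points further from the truth than the completer test, which is why both should be reported.
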